Consistent data support the use of a 7,000-8,000 step per day goal to achieve current recommendations for moderate-to-vigorous-intensity PA.[40] In numerous studies, self-selected PA intensity approximates or exceeds the minimum range recommended by the American College of Sports Medicine (ACSM).[41] In contrast, prescribed exercise intensities often result in feelings of displeasure and loss of autonomy, which interfere with the tenets of self-determination theory, thereby limiting uptake and sustainability.[42, 43] Thus, a step-goal based intervention with self-selected intensity is designed to address the unique barriers of this population, avoid undue stress (a common seizure trigger), and encourage uptake and sustainability. Our work and that of others has shown feasibility of remote interventions and wearables in PWE.[28, 44]

Objectives

Aim 1: To assess feasibility (adherence and sustainability) of a telehealth delivered, step-goal based PA intervention as measured by average daily steps achieved compared to steps assigned during the final 4 weeks of the intervention period (adherence) and the final 4 weeks of the maintenance period post-intervention (sustainability).

[figure not shown]
Aim 2: To assess the self-selected intensity distribution of activity in the intervention arm (time spent in objectively-assessed sedentary behavior, light-intensity, or moderate to vigorous intensity activity) to determine if they achieve intensities within the American Heart Association (AHA) guidelines.

Exploratory Aim 3: To explore estimates of variability of the effect size of a telehealth delivered, step-goal based PA intervention on seizures (measured by frequency and severity) and epilepsy-associated comorbidities (anxiety, depression, QOL, and measures of fitness/cardiovascular health) in the exercise group compared to the control group.

Methods and Measures

Design

A randomized, controlled trial with a two-arm, parallel group design with a wait-list education control

Protocol version:

Template updated 9.24.14

Setting

Academic medical center, Atrium Health Wake Forest Baptist

Subjects selection criteria

Adults with epilepsy will be actively recruited from the Comprehensive Adult Epilepsy Clinic at Atrium Health Wake Forest Baptist, and passively recruited from the community

Inclusion Criteria

- Age 18 or older

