1. **Introduction and ice breaker:** Participants will engage in brief tasks requiring self-disclosure as a means of opening communication for the remainder of the session.
2. **Didactic content:** Next, the coach will guide participants through weekly didactic content related to health and physical activity. These sessions are designed to reduce negative outcome expectancies related to activity (e.g., activity is unsafe, addressing how different types of movement improve health), to highlight facilitators in the environment while addressing common barriers to activity, and providing education on how activity improves health.
3. **Discussion:** Building on weekly didactic content, each session will end with a guided discussion designed to provide positive reinforcement of weekly successes, opportunities to address barriers as a group, and repertoire-development in which participants share exercise experiences they have enjoyed recently.

In addition to weekly group sessions, participants will communicate briefly one-on-one with the behavioral coach using a medium of their choosing (webex, telephone, email) to address any private concerns and to review and revise goals. Key facets of these exchanges include:

1. **Review of the previous week's goal:** The coach will review with the participant progress toward the previous week's goal. To do this, the coach will log into the Garmin Connect website using the credentials provided to the participant by the study team. The coach will emphatically congratulate goal success—thus enhancing self-efficacy through mastery experiences—and adopt a proactive tone during failures with the aim of mitigating feelings of guilt. During week 1, the conversation will instead center on understanding previous experiences with activity to guide selection of the initial goal.
2. **Selection of a new goal:** Participants will aim to progress in both intensity and duration over the course of the program. The participant and coach will select a progressive stepping goal that is challenging but attainable (increase in ~20-30% increments depending on baseline steps). They will objectively self-monitor progress toward step goals, a key self-regulatory behavior. Achievement of goals is a key *mastery experience*, the most potent input to self-efficacy, and consistently identified as the key behavioral predictor of activity behavior.[46]. Goals will be revised weekly until at least 8000

Protocol version:

Template updated 9.24.14

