- **Facilitators:** The coach will include purposeful discussion of environmental and social facilitators during each session.

To ensure fidelity, the coach will audio/video record each group session, and these sessions will be spot checked by a member of the research team using a coaching checklist to ensure each theoretical element is being addressed. The coach will also self-rate adherence to these principles on a checklist following each session. This will serve as a second fidelity check, but will also continuously remind the coach of these important coaching principles.

The use of the Garmin for Goal Review and Selection

Prior to the start of the 1:1 session, the coach will sign into the Garmin Connect web page for the participant using the credentials provided to the participant from the study team. The coach will review step data and any exercise bouts ahead of time to estimate whether the participant achieved the previous week’s goal. This will provide a sense of familiarity to the participant

Protocol version:

Template updated 9.24.14

during the phone call, and will also prepare the coach to troubleshoot Garmin usage for days with missing data.

Arm 2 Control:

Participants randomized to the wait-list attention control group will continue to undergo standard care for 12 weeks. They will continue to wear the Garmin activity tracker and can view their activity but will not be given an exercise program. They will be contacted by a study staff member via telephone every 2 weeks for health education. If for some reason they need to miss a session, the information will be emailed to them. During this time, they will review resources and healthy lifestyle guidelines for people with epilepsy, including healthy diet, medication compliance, seizure precautions, stress management, and sleep hygiene. At the end of study, if they complete all study visits, they have the opportunity to receive a personalized exercise program.

Changes to anti-seizure therapy (including medications or devices) during the study will be discouraged in both groups. However, participants who do report medication or device changes will be allowed to continue in the study but will be analyzed separately in the results. Medications and medication compliance will be reviewed at each study visit.

Strategies to support fidelity of the intervention:

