Appendix

1. Copies of each questionnaires or surveys that will be used
 - a. AEP
 - b. PSS
 - c. NDDI-E
 - d. GAD-7
 - e. QOLIE-31
 - f. EXSE
 - g. EGS
 - h. MOEES
 - i. Exercise Satisfaction Survey
 - j. Exit Survey
 - k. Liverpool seizure severity scale
 - l. PSQI
2. Consent form
3. Study Overview Handout
4. Crisis Procedures – Appendix A
5. Control group scripts:
 - a. Healthy eating script,
 - b. Medication script
 - c. Emotional Health script
 - d. Stress script
 - e. Sleep script
 - f. Seizure diary script
6. Garmin Operating Instructions
7. ActivPAL log and operating instructions
8. Telephone screening script
9. Study Advertisement
10. Study Diary
11. Coaching manual for the intervention group
12. Webex instructions
13. Handout for group instructions after randomization

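### A seizure diary script is listed for the control arm only and its education calls follow baseline, so seizure recording may shift in one arm; the Aim 3 comparator also needs one consistent label

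*Combined protocol and SAP*

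**What the plan says.** **Control arm.** Under Interventions and Interactions, Arm 2 Control: "They will be contacted by a study staff member via telephone every 2 weeks for health education". The topics named there are "healthy diet, medication compliance, seizure precautions, stress management, and sleep hygiene". The schedule table places these calls in the control column of the intervention period, weeks 5 to 16, after randomisation at week 4.

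**Scripts.** Appendix item 5, headed "Control group scripts", lists six: healthy eating, medication, an "Emotional Health script", stress, sleep and a "Seizure diary script".

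**Exercise arm.** In the weekly group session "the coach will guide participants through weekly didactic content related to health and physical activity". The description goes on to outcome expectancies, barriers, facilitators and step goals. It mentions no instruction on keeping the seizure diary.

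**Comparison.** Exploratory Aim 3 looks at seizures and comorbidities "in the exercise group compared to the control group". Under Outcome Measure(s), change in seizure frequency is the diary count in the last four intervention weeks against the count in the four-week baseline. The Analytical Plan regresses change scores on arm and baseline score, and uses the estimates to plan and power a larger trial.

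**Comparator label.** The Design section names a wait-list education control. Arm 2 Control calls it an attention control and says its participants remain on standard care.

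**The concern.** The seizure endpoint is a self-reported count, so the diary is the measuring instrument. If one arm is taught to use it after the baseline count is complete, that arm's later count may differ from its baseline because recording changed, not because seizures did. The teaching goes with assignment, so the difference enters the between-arm estimate directly.

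The comparator label is a related, smaller matter. Several control topics bear on outcomes that Aim 3 compares. A reader planning the larger trial who takes the comparator to be standard care would misread what the estimate contrasts.

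**Working it through.** The plan states no effect size, SD or power for Aim 3, so there is no figure of its own to reproduce.

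**1. Timing.** Baseline is the four weeks before randomisation at week 4. The intervention period is weeks 5–16, so its last four weeks are weeks 13–16. Calls every two weeks for 12 weeks give 12 / 2 = 6 calls, which matches the six scripts. Any script used in these calls is therefore delivered after the baseline count. The order is not stated. If the calls followed the listed order, the diary script would come in the sixth call, in week 15 or 16, and would touch only part of the final window. If it came earlier, it could affect all of it.

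**2. Effect on the planned estimate.** Let μ be the expected recorded count in the final four weeks without the script, equal in both arms (no true effect). Let g be the relative change in control recording over that window. Randomisation balances the baseline count, and the script comes after it, so the expected arm coefficient (exercise minus control) is

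μ − (1 + g)μ = −gμ seizures per four weeks.

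The baseline term does not change this, because g arises after baseline and in one arm only. As a rate ratio, exercise to control, it is 1 / (1 + g):

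- g = 0.10 (assumed): 1 / 1.10 = 0.909, an apparent 9% lower rate.
- g = 0.20 (assumed): 1 / 1.20 = 0.833, an apparent 17% lower rate.
- g below zero, for example if the script narrows what participants count as a seizure: the sign reverses and exercise looks worse.

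The documents give no value for g. The range only shows how a recording change carries through.

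**3. Overlap of the other control topics with exploratory outcomes.**

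| Script | Related outcome | Named in the Aim 3 change-score list? |
|---|---|---|
| Medication | AEP and seizure frequency, indirectly; compliance is not itself an outcome | Yes |
| Emotional health | NDDI-E, GAD-7 | Yes |
| Stress | PSS | No, an exploratory endpoint only |
| Sleep | Total sleep time; PSQI | Total sleep time yes; PSQI no |
| Healthy eating | None | – |

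**4. Why the label matters for planning.** Suppose coaching is worth 0.5 SD against no education, and the education itself 0.1 or 0.2 SD (both assumed). The expected estimate is then 0.4 or 0.3 SD. With n per arm = 2(1.96 + 0.84)² / d² for a 1:1 trial at 80% power and two-sided 5%, the requirement is 63 at d = 0.5, 99 at 0.4 and 175 at 0.3. Each is right for its own comparator, and the error lies in using one for the other. With 40 participants split about 27:13, the SE of a standardised difference is √(1/27 + 1/13) = 0.34 and the 95% half-width is 0.66, so the pilot cannot show which situation applies.

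**The case against.** The strongest reply is that an education control is a declared and legitimate design. The Design section says so, and Aim 3 claims only a comparison with the control group. This stands. A reader might infer that the whole control package invalidates Aim 3, or that arm 1 must be given all six scripts. The documents do not support that. Coaching versus education is a valid contrast if so labelled. Adding education to arm 1 would alter the package whose adherence and acceptability Aims 1 and 2 assess, and would widen its existing contact advantage of weekly groups plus individual sessions over six calls.

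Second, the script texts and the coaching manual are listed but not reproduced. Arm 2 Control mentions seizure precautions and not diary keeping, while the Appendix has a diary script and none on precautions, so the diary script may contain something other than recording instructions. This also stands. A reader might infer that arm 1 certainly receives no such content; the text shows only that none is described.

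Third, both arms share diary safeguards: distribution at Visit 1, no randomisation below 75% complete baseline days, daily reminders, weekly staff review, and a call when a diary is missing. These lower the risk. They act mainly on whether diary days are returned, less on what a participant records as a seizure on a given day, so they do not exclude a shift in one arm.

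**Conclusion.** The point holds in a limited form. A diary script is assigned to controls alone, the control education calls fall between the two counts that form the seizure endpoint, and no section gives arm 1 an equivalent. That opens a route to differential measurement change that the planned model cannot correct. It assumes that the script is delivered in those calls and that it affects recording.

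The size is unknown. A reader might take the 9–17% as the expected bias, or conclude that exercise will be falsely favoured. Neither follows: the 10–20% capture gain is assumed, and the direction depends on a script that is not shown. The consequence is confined to exploratory Aim 3 and the planning that rests on it. The inconsistent comparator label is a matter of wording that affects how those estimates are carried forward.

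**What to change.** 1. Give the seizure diary script to all participants at Visit 1, when the diary is distributed, so that recording is standardised before the baseline count. Then drop it from the control-only calls, or repeat it identically and on the same timetable in both arms.
2. Describe the Aim 3 contrast throughout as step-goal coaching versus epilepsy health education. Reconcile the standard-care wording in Arm 2 Control with the Design section, and carry that label into planning of the larger trial. This applies to batches already treated as well.
3. Giving arm 1 the remaining scripts is an optional design choice, not a required correction.

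The cost is a short amendment that uses an existing document. The downside is a small difference in diary instruction between earlier and later batches, which should be stated when the seizure results are reported. Aims 1 and 2 are unaffected.

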At the end of the intervention period, participants will return for post-intervention assessments to include assessments of seizure frequency (Study Diary), seizure severity (Liverpool Seizure Severity Scale), depression(NDDI-E), Review Assurance of the NNDI-E, anxiety (GAD-7), quality of life (QOLIE-31), medication side effects (AEP) cardiorespiratory fitness and mobility (maximum oxygen uptake and 6 minute walk test), sleep (PSQI and from Garmin device) and autonomic tone (heart rate variability).

At the end of the intervention period, participants in arm 1 will be encouraged to continue their current habits. Participants in arm 2 will be offered the opportunity to receive a personalized exercise program. Those in arm 1 will also complete a questionnaire about the acceptability, tolerance and satisfaction with the exercise intervention.

Visit 4, Week 28. Sustainability Follow-up and Study end

This will be a remote visit in order to reduce exposure in the era of COVID-19 as well as improve access for PWE. All outcomes will be re-assessed for sustainability, with the exception of the exercise test, HRV and the 6MWT due to the remote nature of this visit. The risks of excessive in-person visits and transportation issues outweigh the potential benefit of collecting this follow-up data, especially in light of COVID-19. At the end of the visit, all participants will answer an exit questionnaire on their thoughts about the study, what they liked, and what they would change.

All visits will occur either at the Worrel Building or at the Clinical Research Unit (CRU). Due to batched enrollment, time between visits (especially Visits 2 and 3) may vary.

	Visit 0 Telephone Screen	Visit 1 Enrollment Week 0	Visit 2** Randomization Week 4	Intervention Period Week 5-16		Visit 3 End Intervention Week 16	Visit 4 Follow-up Week 28 (remote)
				Exercise	Control		
Review inclusion/exclusion	X	X					
10 meter walk screen		X					
Informed Consent		X					
Vital Signs		X				X	
Collect demographic and baseline medical information		X					

Protocol version:

Template updated 9.24.14

Distribute Study Diary		X					
Distribute Activity Tracker		X					
Collect/Review Study Diary*			X			X	X
Collect/Review data from Garmin			X	X	X	X	X
Review medications and adherence		X	X			X	X
Randomization			X				
Weekly telehealth coaching				X			
Intervention satisfaction questionnaire				X			
Telephone education Q2 weeks					X		
Exercise Test			X			X	

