3. Exploratory Objectives: Exploratory Effectiveness: For exploratory efficacy purposes, we will also gather pre- and post- intervention data on seizures, depression, anxiety, physical functioning, quality of life, and social cognitive mediators of behavior change via the following:

a. Exploratory Endpoints

i. Effects on seizures

1. Seizure frequency via study diary report

This has been shown to be a reliable and standard way of recording seizures in epilepsy studies. For the purposes of evaluating a change in seizure frequency, the number of seizures during the final 4 weeks of the intervention will be compared to the number of seizures during the 4-week baseline. The diaries will be returned via electronic data capture in redcap. Participants will be reminded to complete and return the diary via automated text and/or email. If diaries are not received, the participant will be called and prompted to return the study diary.

2. Seizure severity via the Liverpool seizure severity scale (LSSS)

ii. Effects on mood:

1. Depression scores

Participants will complete the Neurological Disorders Depression Inventory for Epilepsy (NDDI-E)[47]. This will be performed in-person at visits 1 and 3 only (monitoring and management of expression of suicidal ideation is outlined under Section VI below). This will be reviewed by study personnel and documented in the *Review Assurance of the NNDI-E* form

2. Anxiety scores

Participants will complete the Generalized Anxiety Disorder (GAD-7)[48, 49] in person at Visits 1 and 3 and remotely via redcap survey at Visit 4.

3. Stress scores (PSS)

Participants will complete the Perceived Stress Scale (PSS) in person at Visits 1 and 3 and remotely via redcap survey at Visit 4.

iii. Effects on quality of life

1. Quality of Life

Participants will complete the Quality of Life in Epilepsy-31 (QOLIE-31)[50]. This will be given in person as Visits 1, and 3, and remotely via emailed redcap survey link at Visit

2. Medication side effects

Participants will complete the Adverse Event Profile (AEP) at Visits 1 and 3 and remotely via emailed redcap survey link at Visit 4

iv. Effects on social cognitive theory constructs

1. To evaluate the influence of social cognitive constructs on behavior change in this population, participants will complete the Exercise Self-

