Aim 1 To assess Feasibility, we will look at (1) adherence and (2) sustainability. Adherence, defined as the proportion of participants who achieve their assigned step goal (as measured by average daily steps via the Garmin device) over the last 4 weeks of the intervention period, will be calculated and 95% binomial confidence intervals generated. Sustainability will be calculated similarly for the final 4 weeks of the maintenance period. In each case, we will utilize a one-sided 95% confidence interval to estimate the lower bound for adherence and sustainability rates to inform future studies.

Aim 2 To assess exercise *intensity*, we will use descriptive statistics to describe the time spent in sedentary, light, and moderate to vigorous PA. We will generate confidence intervals to evaluate if the achieved intensity is within the range recommended by the AHA (150 min of moderate or 75 min of vigorous activity per week).[59] To assess acceptability, arm 1 will answer a questionnaire at the end of the 12 week intervention about the acceptability, tolerance and satisfaction with the exercise intervention. For the main endpoint, we will use the question “How satisfied were you with the exercise intervention?” with scale of 1=VERY UNSATISFIED, 2=UNSATISFIED, 3=NEUTRAL, 4=SATISFIED, 5=VERY SATISFIED. We will calculate the proportion of subjects who answer 4 or above.

To address Aim 3 (exploratory evaluation of effects epilepsy and epilepsy associated comorbidities), we will compute change scores in seizure frequency, severity (LSSS), anxiety (GAD-7), depression (NDDI-E), medication side effects (AEP), cardiorespiratory fitness (VO2 max and 6MWT), heartrate variability (HRV), sleep (total sleep time per night) and quality of life (QOLIE-31) pre- and post-intervention. We will use multivariable linear regression models modeling change score as the outcome, with intervention assignment as the main effect of interest and baseline scores as a confounding variable. We will use estimates of the effect sizes and variability for planning and power of a larger trial. For HRV parameters, we will look at high and low frequency indices, standard deviation of normal-to-normal interval (SDNN) and the root mean square of successive differences (RMSSD) indices, given their established study in PWE.[11, 12]

Similarly, we will explore for effects on social cognitive mediators of behavior change (scores on EXSE, MOEES, and EGS), following the same modeling approach.

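### Participants who change anti-seizure therapy are to be analysed separately and no analysis set is named, so on the most natural reading they leave the Aim 3 comparison, which can modestly bias its planning estimates

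*Combined protocol and SAP*

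**What the plan says.** The rule on therapy changes is in Interventions and Interactions, at the end of the Arm 2 Control text, but it covers both arms: "Changes to anti-seizure therapy (including medications or devices) during the study will be discouraged in both groups". It goes on to say that "participants who do report medication or device changes will be allowed to continue in the study but will be analyzed separately in the results". It does not say what separate analysis means, which outcomes it covers, or whether the timing of the change matters.

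The Analytical Plan does not mention therapy changers and names no analysis set for any aim. For Aim 3 it fits linear regressions of the pre-to-post change score, "with intervention assignment as the main effect of interest and baseline scores as a confounding variable". The purpose is stated next: "We will use estimates of the effect sizes and variability for planning and power of a larger trial". The Aim 3 outcomes include seizure frequency, seizure severity (LSSS) and medication side effects (AEP). For seizures, "the number of seizures during the final 4 weeks of the intervention will be compared to the number of seizures during the 4-week baseline", so a therapy change can come before the outcome window. The Blinding section says that participants know their arm.

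**The concern.** Two statisticians working from this document could produce different Aim 3 estimates. One, following the therapy-change rule, would take changers out of the between-arm model. The other, following the Analytical Plan, would keep everyone by assignment.

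The first choice selects on an event that can occur after randomisation. A change of medication or device may be prompted by seizures or side effects, which are themselves Aim 3 outcomes. It may also be prompted by knowing the assigned arm. Participants without a change need not then be comparable between arms, and the spread of their outcomes is narrower than in the whole group. Both the effect size and the SD are to be carried into the power calculation of a larger trial, so that trial could be planned too large or too small.

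The link is most plausible for seizure frequency, LSSS and AEP. The documents give no basis for sizing it for VO2 max, the 6-minute walk, HRV or sleep.

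**Working it through.** The plan has no figure to reproduce: it gives no therapy-change rate, SD, effect size or power. What follows is an illustration in the plan's own type of model.

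**From the documents.** Up to 40 enrolled, allocated 2:1 (Sample Size), so at most about 27 v 13. The model is change score on arm plus baseline (Analytical Plan). Its arm coefficient equals that of follow-up score on arm plus baseline.

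**Assumed.** All 40 are randomised. Baseline B and follow-up Y have SD 1 in each arm and correlate 0.6. Mean Y is 0 in controls and −d with exercise (lower is better). Tendency to change is L = ρY + √(1−ρ²)e, with ρ = 0.3 or 0.6, and a participant is removed if L > c. Changing therapy has no effect on Y.

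**Formulas.** Let h(x) = φ(x)/Φ(x), with a = c in controls and a = c + ρd with exercise. Among those kept in an arm with mean m, and with w = h(a)² + a·h(a):
- mean Y = m − ρh(a); mean B = −0.6ρh(a)
- var Y = 1 − ρ²w; var B = 1 − 0.36ρ²w; cov = 0.6(1 − ρ²w)
- slope b = pooled cov / pooled var B
- adjusted difference = ΔY − bΔB, control minus exercise
- residual variance = var Y − cov²/var B

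**Standard error, nobody removed.** √(1/27 + 1/13) = 0.338 SD unadjusted. Times √(1 − 0.36) = 0.8, this is 0.270 SD adjusted.

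**1. True difference 0.50, same mechanism in both arms, 20% of controls removed** (c = 0.842; exercise removed 16% or 13%).
- ρ = 0.3: ΔY = 0.482, b = 0.586, adjusted difference 0.488, residual SD 0.791.
- ρ = 0.6: ΔY = 0.433, b = 0.548, adjusted difference 0.455, residual SD 0.765.
- The residual SD with nobody removed is 0.800. The bias is 0.012 or 0.045, that is 4% or 17% of 0.27.
- Later-trial size ratio, (0.5/0.8)² ÷ (difference/residual SD)²: 1.02 or 1.10, so about 2% or 10% too large.

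**2. No true effect, unequal change rates.**
- 10% v 30%: h = 0.195 and 0.497, a gap of 0.302. The false difference is ρ × 0.302 × (1 − 0.6b), with b = 0.588 or 0.550: 0.059 or 0.121 SD (22% or 45% of 0.27).
- 5% v 15%: h = 0.109 and 0.274, giving 0.032 or 0.066 SD.
- The sign depends on which arm changes more.

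**3. No true effect, 20% removed from each arm.** There is no bias in the difference. Here w = 0.350² + 0.842 × 0.350 = 0.417.
- ρ = 0.3: residual variance 0.624 against 0.640, ratio 0.976.
- ρ = 0.6: residual variance 0.575 against 0.640, ratio 0.898.
- A later trial sized on this SD would be about 2% or 10% too small.

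A simulation of the adjusted model agreed with all three sets of results.

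**Sensitivity to assumptions.** An unadjusted simulation moved the tendency to change by the full treatment effect instead of ρd, with correlations of 0.3 to 0.7, control change rates of 10% to 30% and true differences of 0.3 or 0.5. The difference then moved toward zero by 0.02 to 0.15 SD and the later-trial size ratio ran from 1.13 to 1.71.

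**The case against.** **The wording does not say excluded.** Changers stay in the study, and a by-assignment main model with a separate presentation of changers would satisfy both sections. A reader might infer that the document flatly contradicts itself or orders exclusion; it does neither. What stands is that the milder reading is not written anywhere, and under it the plan still fails to say which analysis is the main one.

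**Bias presupposes an estimand.** Therapy changes are made to alter seizures, and the illustrations assume that they have no effect. If changing gave an assumed benefit of 0.5 SD and rates were 10% v 30%, keeping everyone would give an arm difference of 0.5 × (0.30 − 0.10) = 0.10 SD with no exercise effect at all. That is a fair limit on what the all-randomised estimate means: it is the effect of assignment, not of exercise alone. It does not rescue exclusion, because dropping participants on a post-randomisation event does not validly estimate the effect of exercise without therapy change either.

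**The sizes come from modelling choices.** This is true. The direction of the planning error also differs between scenarios 1 and 3. A reader who leaves out the baseline adjustment would get 0.09 or 0.18 SD in scenario 2 at 10% v 30%, but the plan's model adjusts for baseline and those figures overstate it.

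**Later changes.** The rule speaks of changes during the study, and Visit 4 is at week 28. A reader might infer that a change after Visit 3 removes someone from a comparison already completed at week 16. That needs a very literal reading, since Aim 3 is defined pre- to post-intervention, and the point does not rest on it.

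**Conclusion.** The concern holds. The plan states a handling rule based on an event that can follow randomisation, names no analysis set, and nowhere keeps changers in the main Aim 3 model. Followed as it most naturally reads, the rule can bias the arm difference and shrink the SD intended for planning.

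The likely size is modest, but it cannot be derived from the documents, which give neither a change rate nor reasons for change. Under the assumptions shown, every adjusted bias is less than half of this study's adjusted standard error of 0.27 SD, and the later-trial size is off by about 2% to 10% in either direction. Other assumptions give larger or smaller values.

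A reader might infer that the feasibility result is also compromised. The documents do not support that on this argument: Aim 1 is a proportion within the exercise arm, with no randomised contrast to undo. Aim 3 is labelled exploratory. The point is worth correcting because supplying planning estimates is the stated use of Aim 3 and the correction is cheap, not because the trial's main conclusions depend on it.

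**What to change.** In the Arm 2 Control text, replace only the closing clause about separate analysis. Leave the statements that changes are discouraged and that changers may continue. State there and in the Analytical Plan under Aim 3:

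*The main Aim 3 analysis includes all randomised participants with outcome data in their assigned arm, regardless of changes in anti-seizure medication or device. Changes are tabulated by arm and timing, and a supportive sensitivity analysis excludes participants whose therapy changed between randomisation and Visit 3.*

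The cost is two short text edits, one table and one sensitivity analysis. No visits are added: the schedule row "Review medications and adherence" is already marked at Visits 1, 2, 3 and 4. Device changes rest on participant report, so their dates should be recorded. Tying the window to Visit 3 instead of a fixed week suits the batched enrolment, which lets the interval between Visits 2 and 3 vary.

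The downside is that the main estimate includes any effect of therapy changes and should be described as the effect of assignment. The sensitivity analysis carries the selection risk described above and is supportive only.
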